7.7.3 Vital Signs

The following vital signs will be listed and summarized by treatment group and visit.

- Supine SBP and DBP (mm Hg)

- Pulse rate (beats/min)
- Respiration rate (breaths/min)
- Body temperature (°C)

Vital signs data and changes from Baseline in vital signs will be summarized by visit using standard descriptive statistics for the Safety population.

The Baseline value will be defined as last scheduled or unscheduled value collected prior to the first dose of treatment. For analysis by visit, nominal study visits will be used.

7.7.4 Electrocardiograms

The following quantitative ECG measurements will be listed and summarized by treatment group and visit for the Safety population:

- heart rate (beats/min);
- PR interval (ms);
- QRS interval (ms);
- QT interval (ms);
- Fridericia corrected QT (QTcF) interval (ms)

An overall Investigator assessment of ECG will be summarized and listed using categories reported in the eCRF.

7.7.5 Physical Examination

Physical examination results (normal or abnormal) and details of abnormalities will be listed for each subject.

For each physical examination body system, the number and percentage of subjects with abnormalities at Baseline and post-Baseline will be summarized by treatment group for the Safety Population.

7.8 Pharmacokinetic Analysis

The population pharmacokinetic analysis was described in a separate analysis plan: Final Population Pharmacokinetic Analysis and Report Plan, dated as of February 22, 2019.

Pharmacokinetic plasma concentration of TMX-049 will be summarized and listed by treatment group using descriptive statistics (including geometric mean and CV%, arithmetic mean, SD, arithmetic CV%, median, observed maximum, minimum, and N). No formal statistical tests are planned.

The following rules will be applied if there are values that are below the limit of quantification (BLQ) or if there are missing values (eg, no result [NR]) in a plasma concentration data sets to be summarized.

- For the calculation of summary statistics, BLQ values will be set to zero.
- If an embedded BLQ value is considered anomalous within the concentration time profile, this value will be excluded from the summary statistics.
- Where there is NR, these will be set to missing.
- If values are obtained from more than or equal to 50% subjects, the summary statistics will be calculated.
- If values are obtained from less than 50% subjects, all arithmetic and geometric summary statistics will be denoted as NC.

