3.3 Safety Variables

The safety endpoints include:

- Proportion of subjects with reported adverse events (AEs), discontinuation due to AEs and serious adverse events (SAEs)
- Proportion of subjects with AEs considered by the Investigator to be related to study drug
- Proportion of subjects with mild, moderate, or severe AEs as assessed by the Investigator
- Changes from Baseline in vital signs, ECGs, and laboratory parameters

4. Pharmacokinetic/Pharmacodynamic variables

The Pharmacokinetic endpoint is the plasma concentrations of TMX-049 at Study Weeks 2, 6, and 12/ET.

5. Analysis populations

Unless otherwise specified, all efficacy analyses will be performed using the modified Intention-to-Treat (mITT) population, all sensitivity analyses will be

performed using the Per Protocol (PP) population and safety analyses will use Safety population. Pharmacokinetic (PK) analyses will be performed using the PK population.

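### SAP 7.8 sets BLQ concentrations to zero for every summary statistic but also requires a geometric mean and geometric CV%, which a retained zero makes 0 and undefined

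*SAP*

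**What the plan says.** SAP Section 7.8 (Pharmacokinetic Analysis) asks for descriptive statistics of TMX-049 concentration by treatment group, "including geometric mean and CV%, arithmetic mean, SD, arithmetic CV%, median, observed maximum, minimum, and N". Because the arithmetic CV% is listed separately, the CV% paired with the geometric mean is read here as the geometric CV%.

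The section then gives five data rules:

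- BLQ results: "For the calculation of summary statistics, BLQ values will be set to zero".
- Anomalous BLQ results: "If an embedded BLQ value is considered anomalous within the concentration time profile, this value will be excluded from the summary statistics".
- Samples without a result: "Where there is NR, these will be set to missing".
- Well-filled cells: "If values are obtained from more than or equal to 50% subjects, the summary statistics will be calculated".
- Sparsely filled cells: "If values are obtained from less than 50% subjects, all arithmetic and geometric summary statistics will be denoted as NC".

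SAP Section 4 sets the time points: "The Pharmacokinetic endpoint is the plasma concentrations of TMX-049 at Study Weeks 2, 6, and 12/ET". Protocol Section 7.10.5 says only that concentrations are listed and summarised, and it adds no BLQ rule. Neither document states an LLOQ.

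**The concern.** A geometric mean and a geometric CV are calculated on the log scale, and zero has no logarithm. The zero rule is written for summary statistics in general, and the list of statistics includes two that cannot accept a zero. Followed literally, the plan gives a geometric mean of 0 and no geometric CV. Followed through a program that drops the log of zero, it gives statistics on a subset that the SAP does not define, beside an N that belongs to the arithmetic row.

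Describing PK in this population is a secondary objective (Protocol Section 6, SAP Section 2.1), and the geometric mean is a usual summary for concentrations. What is at stake is whether those table entries can be read and reproduced.

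**Working it through.** The documents state no figure on this point, so there is none to reproduce. The check follows from the definitions.

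**Inputs.** The rules and statistics come from SAP 7.8. For illustration, a cell has n = 40, the approximate group size in SAP 2.3. That figure refers to the primary endpoint analysis, so the PK cells may differ. The LLOQ and BLQ rate are not stated.

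**1. Geometric mean.** GM = (x₁ × x₂ × … × xₙ)^(1/n). With one xᵢ = 0 the product is 0, so GM = 0^(1/40) = 0, whatever the other 39 values are. More zeros change nothing.

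**2. Geometric CV.** gCV% = 100 × √(exp(s²) − 1), where s² is the variance of ln x. As ln 0 does not exist, s² and the gCV are undefined.

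**3. Other statistics.** Arithmetic mean, SD, median, minimum and maximum can all be calculated with zeros present. So can the arithmetic CV%, unless every value is zero. The conflict is confined to the two geometric entries.

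**4. If software drops the log of zero.** With k BLQ values, the geometric row uses 40 − k subjects and the arithmetic row uses 40. That is 39 against 40 for k = 1, and 36 against 40 for k = 4. SAP 7.8 lists a single N.

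**5. Do the other rules repair this?**

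- *Exclusion of an anomalous embedded BLQ.* This removes a value only when it is judged out of place in a concentration-time profile. The trial schedules one sample at each of three visits, and Protocol 7.7.2 calls the sampling sparse. A BLQ value not judged anomalous stays in as zero.
- *The 50% rule.* The SAP does not say whether a BLQ result counts as a value obtained. If it does not count, a cell of 40 with 20 BLQ has 20/40 = 50% and is still calculated; with 21 BLQ it has 19/40 = 47.5% and is shown as NC. So 1 to 20 zeros remain in calculated cells. If BLQ does count, the rule screens out even fewer.
- *The NR rule.* Results that are absent become missing while BLQ results become zero. The plan therefore means BLQ values to enter the calculation.

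**6. How many BLQ values are needed?** One. The chance of at least one in a cell of 40 is 1 − (1 − p)^40, assuming independent samples with BLQ probability p. The rates below are assumptions to show the range, not predictions.

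| Assumed p | Chance of at least one BLQ in 40 |
|---|---|
| 1% | 33% |
| 2% | 55% |
| 5% | 87% |
| 10% | 99% |

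**7. Plausible sources.** The Visit 4 sample is a pre-dose trough (Protocol 7.7.1). Missed doses are foreseen (Protocol 7.4.1). The last PK time point pools Week 12 with early termination (SAP Section 4), and subjects who have permanently stopped study drug are asked to attend that visit (Protocol 7.5.5).

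**The case against.** The best defence is that the effect is small and unknown. SAP 7.8 also reports the arithmetic statistics, the median, the range and listings. No formal PK tests are planned, and the population PK analysis is governed by a separate plan dated February 22, 2019. The run-in admits only subjects with at least 80% compliance, which should limit missed doses. Visit 6 may hold an elimination-phase, trough or t_max sample (Protocol 7.7.1), so its geometric mean is hard to interpret however BLQ values are handled. The table shells mentioned in SAP 7.1 are not among the documents and might carry a footnote on the geometric n. All of this stands as a limit on importance. None of it reconciles the two instructions in SAP 7.8.

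Three stronger readings are tempting, and the documents do not support them.

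- *That every cell with a BLQ sample fails.* A BLQ excluded as anomalous never enters the cell, and a cell under the 50% threshold is reported as NC.
- *That the reported geometric mean will be too high by a known amount.* With no LLOQ, BLQ rate or concentration level for this population, any such figure would rest on assumptions. Taken literally the rule gives 0, which is not too high. Dropping zeros gives the same value as an openly declared quantifiable-only summary; the fault there is that it is undeclared.
- *That the half-life of 10 to 19 hours (Protocol 5.4.3) shows early termination samples will be BLQ.* Neither document fixes the time from last dose to that visit, and without an LLOQ the step to BLQ cannot be made.

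**Conclusion.** The point holds as an inconsistency within SAP 7.8. In any cell where the statistics are calculated and at least one BLQ value is kept as zero, the geometric mean is 0 and the geometric CV is undefined. If the program drops the log of zero, the two geometric entries use a smaller n that the plan does not disclose. This follows from the definitions and rests on one reading: that the CV% beside the geometric mean is geometric.

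The number of affected cells cannot be determined; it could be none. The consequence is limited to the descriptive concentration tables and does not reach the efficacy or safety analyses. It is a minor point, worth correcting because the stated rule gives an unusable result and the correction is easy.

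**What to change.** In SAP 7.8, restrict the zero substitution to the arithmetic mean, SD, arithmetic CV%, median, minimum and maximum. State that the geometric mean and geometric CV% are calculated from quantifiable values only, and show the number quantifiable and the number BLQ beside them.

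The price is that the geometric statistics then describe quantifiable samples only; the displayed BLQ count makes this visible. In the same edit it would help to say whether a BLQ result counts as a value obtained under the 50% rule. A separate summary of early termination samples taken after study drug was stopped is optional.

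The cost is one SAP sentence and a table footnote, with no new data.

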7.9 Interim Analysis

No interim analysis is planned for this study.

8. Changes in Planned Analysis

Not applicable.

Statistical Analysis Plan

Teijin America, Inc.
TMX-049DN-201

9. References

The schedule of study procedures (from the Protocol) is attached for reference.	Screening		Single-Blind, Placebo, Run-in Phase		Double-Blind Treatment Phase				Follow-up
	Visit 1	Visit 2		Visit 3	Start of study drug	Visit 4	Visit 5	Visit 6/ET	Visit 7
Study days and visit window guidelines	Day -42 to Day -15	Day -14 ± 4 days	Day -14 ± 4 days to Day 0	Day 0	Day 1	Day 14 ± 4 days	Day 42 ± 7 days	Day 84 ± 7 days	Visit 6/ET+28 ± 7 days
Administrative Procedures									
Informed consent	X								
Assignment of Screening number	X								
Contact IXRS	X	X		X		X	X	X	X
Check of eligibility based on inclusion/ exclusion criteria	X	X		X					
Assignment of randomization number				X					
Pre-visit telephone reminder for urine and PK ¹		X		X		X	X	X	X
Trial Compliance									
Prior/concomitant medication review	X	X		X		X	X	X	X
Dispense urine collection supplies	X	X		X		X	X	X	
Investigational Product									
Dispense study drug (placebo) for single-blind run-in		X							
Administration of placebo			qd dosing for 2 weeks						
Assess single-blind compliance				X					
Dispense double-blind study drug (placebo or TMX-049)				X		X	X		
Administration of TMX-049 or placebo						qd dosing for 12 weeks			
Assess double-blind compliance						X	X	X	
Clinical Procedures/Assessments									
Demographics and medical history	X								
Height	X								
Body weight	X			X		X	X	X	X
Vital signs (blood pressure ² , pulse rate, and body temperature)	X	X		X		X	X	X	X
Physical examination		X						X	

Statistical Analysis Plan

Teijin America, Inc.
TMX-049DN-201

The schedule of study procedures (from the Protocol) is attached for reference.	Screening		Single-Blind, Placebo, Run-in Phase		Double-Blind Treatment Phase				Follow-up
	Visit 1	Visit 2		Visit 3	Start of study drug	Visit 4	Visit 5	Visit 6/ET	Visit 7
Study days and visit window guidelines	Day - 42 to Day - 15	Day - 14 ± 4 days	Day -14 ± 4 days to Day 0	Day 0	Day 1	Day 14 ± 4 days	Day 42 ± 7 days	Day 84 ± 7 days	Visit 6/ET+28 ± 7 days
12-lead ECG		X						X	
AE monitoring	X	X	X	X					
TEAE monitoring					X	X	X	X	X
Laboratory Assessment									
UACR ³	X								
First morning void UACR		X ⁴		X ^{4,5}		X ^{4,5}	X ^{4,5}	X ^{4,5}	X ^{4,5}
Complete blood count (CBC)	X			X		X	X	X	X
Serum chemistry profile (including sUA and serum creatinine to calculate eGFR)	X	X		X ⁵		X ⁵	X ⁵	X ⁵	X ⁵
Serology: HIV, hepatitis B, and hepatitis C		X							
Thyroid hormones		X		X		X	X	X	X
Lipid panel		X		X		X	X	X	X
HbA1c	X			X				X	
Urine pregnancy (females of childbearing potential)	X			X				X ⁶	X
FSH (females of non-childbearing potential)	X								
Urinalysis	X			X		X	X	X	X
Blood and urine samples for biomarkers ⁷				X		X	X	X	X
Pharmacokinetic sampling						X ⁸	X ⁹	X ¹⁰	
Pharmacogenomics sampling				X ¹¹					

Note:

AE = adverse event; CRF = Case Report Form; ECG = electrocardiogram; eGFR = estimated glomerular filtration rate; ET = early termination; FSH = follicle-stimulating hormone; HbA1c = glycosylated hemoglobin; HIV = human immunodeficiency virus; IXRS = interactive voice/web response system; KIM 1 = kidney injury molecule 1; L FABP = liver fatty acid binding protein; NAG = N-acetyl-β-D-glucosaminidase; PK = pharmacokinetic; 8 OHdG = 8 hydroxy 2' deoxyguanosine; qd = once-daily; sUA = serum uric acid; TEAE = treatment emergent adverse event; tmax = time of maximum observed plasma concentration; UACR = urinary albumin to creatinine ratio.

¹Telephone contact around 3 days prior to scheduled visits.

²Average of triplicate measurements.

³Urine sample for assessment of UACR to be collected at the study site once subjects have signed the informed consent form.

⁴The average of the 2 consecutive day mid stream, first morning void UACR results will be used. The 2 consecutive day first morning void urine samples will be collected at the subject's home the morning before and the morning of each visit.

Statistical Analysis Plan

Teijin America, Inc.
TMX-049DN-201

⁵Results of sUA and UACR will not be reported to Investigators, subjects, and the Sponsor staff.

⁶Only Early Termination Visit.

⁷Urine sample for the analysis of KIM-1, L-FABP, 8-OHdG, and NAG; the mid stream, first morning void urine samples collected by the subjects at home will be used for the analysis of exploratory biomarkers. Aliquots of serum, plasma, and urine will be stored for potential use in other biomarker assays.

⁸At Visit 4, a sample will be obtained prior to TMX-049 dosing (trough sample). The time of PK sample acquisition, the time of dosing prior to the PK sample acquisition, and whether the subject took study medication with or without food should be recorded in the CRF.

⁹At Visit 5, a sample will be obtained 3 ± 1 hours after study medication dosing (tmax sample). The timing of dosing can be adjusted to the time of visiting. The time of PK sample acquisition, the time of dosing prior to the PK sample acquisition, and whether the subject took study medication with or without food should be recorded in the CRF.

¹⁰At Visit 6, a sample will be obtained ≥ 6 hours (the ideal target is ≥ 8 hours) after study medication dosing (elimination phase sample). If a subject cannot visit within the time window, a sample will be obtained when the subject visits, even out of the time window. If the trough sample is not obtained at Visit 4, the trough sample should be obtained at Visit 6, instead of the elimination phase sample. If the trough sample is obtained at Visit 4 and tmax sample is not obtained at Visit 5, the tmax sample should be obtained at Visit 6, instead of the elimination phase sample. The time of PK sample acquisition, the time of dosing prior to the PK sample acquisition, and whether the subject took study medication with or without food should be recorded in the CRF.

Sites have the option to have a study participant return to the site on a separate day to obtain a properly timed Visit 4, 5, or 6 sample for PK analysis.

¹¹Sample will be obtained only from subjects that consent to pharmacogenomics sampling.
